#### Device Description:

The EUM300 is composed of three units: Disposable electrode, Maternal unit and Interface unit.

Disposable electrode applied part – Proprietary bio-compatible patch electrode array with nine Ag/AgCl and hydrogel connections. Electrode is made by US based manufacturers: Lead-Lok, Sandpoint, ID and Molex, Naperville, IL.

Maternal Unit – The maternal unit is connected via a proprietary connector to the electrode. The EMG signals are amplified by an analog front-end. OB-Tools Algorithm runs on a DSP board and the result – Fetal Heart Rate and Uterine Activity are transmitted via Bluetooth. The unit contains a 4.2V Li-Ion rechargeable battery. The battery allows 24h of work and must be charged away from the patient.

Interface unit – Wall mount unit translates the information received from a paired Bluetooth Maternal unit. In this setup the EUM is used as a secondary system, one that

Version 5.13; June 19, 2020

is not involved with clinical decisions. In this case a PC computer receives the bluetooth transmission from the maternal unit and saves it into an Excel readable file. A primary monitor that is used for clinical decisions may also be connected to the PC and its data is recorded into the same file for comparison. The file format is a simple 6 column format: Date, Time, EUM UA, EUM FHR, Monitor UA, Monitor FHR. The file can be read and analyzed using Excel, Matlab and other statistical tools.

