#### Objectives:

Version 5.13; June 19, 2020

1. Compare the contraction tracings obtained using the EUM device vs. those obtained using the intrauterine pressure catheter vs. those obtained from external tocodynamometer among current obese patients (BMI greater than 30 kg/m^2) and nonobese patients using simultaneously obtained, 30 minute tracings with regards to the frequency of contractions, the duration of contractions, maximum height of the contractions, the total Montevideo units recorded, the timing of the contractions, and the amount of discontinuous tracings from the devices. Of the variables mentioned, the Montevideo units will only be comparable between the IUPC tracings and the EUM device.
2. Compare the fetal heart rate tracing obtained via the EUM device vs. external fetal Doppler vs. fetal scalp electrode (simultaneously obtained, 30 minute tracings will be compared) among obese patients and nonobese patients with regards to the amount of discontinuous/uninterpretable tracing, average fetal heart rate, baseline heart rate, the number accelerations, the number of decelerations, the timing of the accelerations, the timing of decelerations, the maximum fetal heart rate achieved during acceleration, the lowest fetal heart rate achieved during deceleration, and compare the degree of variability in the tracing.
3. Compare tracings of productive vs. non-productive contractions in patients presenting to triage to rule out labor (30 minutes of simultaneously obtained tracings of external tocodynamometer and EUM device will be compared) with regards to the frequency of contractions, the duration of contractions, maximum height of contractions, the timing of the contractions and the amount of discontinuous tracings from both devices, as well as changes in cervical exam on the basis of body mass index. Productive contractions are those that cause a change in cervical exam of 1 cm or more, any change in station or change in effacement of 50% or more.

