## Materials and Methods:

This will be a prospective observational study of women presenting for care to Montefiore Medical Center. Patient enrollment will occur during their obstetric triage encounter or on admission to labor and delivery. Patients will be approached if they meet the enrollment criteria. Once informed consent is obtained and the standard methods of fetal and labor assessment are in place the electrodes of the EUM will be attached to the abdominal skin surface. The electrodes will remain in place until delivery or discharge from the hospital if the patient is found not to be in labor and is discharged undelivered.

Patients will be monitored simultaneously with the EUM device and currently used methods (external or internal devices) as clinically indicated by the standard of care. Providers will be blinded to the results of the EUM device and will continue care as per current guidelines using the information obtained from the current monitoring methods. Data from the EUM devices will be captured on a study laptop computer as will data generated by the currently used fetal/uterine monitor to allow for comparison of the two systems. Each patient will serve as her own control for comparison as the data obtained from the two monitoring systems simultaneously will be compared. Patients will be monitored for 30 minutes once they consent in the labor and delivery triage rooms or labor and delivery rooms. Patients will also be asked to complete a device experience and satisfaction survey comparing the methods of monitoring. Assuming the number of minutes of unreadable tracing for the EUM is less than the Doppler by 1 minute, the standard deviation of difference in minutes by the two devices is 3 minutes, and there are 2 obstetrician readings per subject, to reach a power of 80% with 0.05 significance level, 39 patients will be needed for our primary outcome as listed below. It is anticipated that within 6-12 months, this number can be reached with recruiting efforts at both Weiler and North campus. To maximize recruitment, the co-investigator will be present daily on L&D and triage to recruit patients.

Maternal demographics to be obtained will include maternal age, ethnicity, BMI, gestational age, current medications, mode of delivery, birth weight, Apgar scores,

Version 5.13; June 19, 2020

newborn outcome, medical history and any antenatal complications, past surgical history, and postpartum course.

Primary Outcomes:

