- Continuity in readings of fetal heart rate (as measured in the number of minutes without a readable tracing in a 30 minute sample tracing) between EUM and fetal scalp electrode and external fetal heart rate monitoring from the same patient
- Continuity in readings of contractions (as measured in the number of minutes without a readable tracing in a 30 minute sample tracing) between EUM, IUPC and external tocodynamometer from the same patient

Secondary Outcomes:

- Compare average frequency of contractions between the monitoring systems
- Compare duration of contraction between the monitoring systems
- Compare maximum height of the contraction between the monitoring systems
- Compare total Montevideo units obtained between the monitoring systems
- Compare the timing of the contraction between the monitoring systems
- Compare average fetal heart rate between the monitoring systems
- Compare baseline heart rate between the monitoring systems
- Compare the number accelerations between the monitoring systems
- Compare the number of decelerations between the monitoring systems
- Compare the timing of the accelerations between the monitoring systems
- Compare the timing of decelerations between the monitoring systems
- Compare the maximum fetal heart rate achieved during acceleration between the monitoring systems
- Compare the lowest fetal heart rate achieved during deceleration between the monitoring systems
- Compare the degree of variability in the tracing between the monitoring systems. Degree of variability will be defined as the correlation between the tracings. The tracings will be broken down into 4 minute intervals and defined as minimal, moderate or marked variability and compared with each other for accuracy and

Version 5.13; June 19, 2020

consistency. Most accurate will be the internal monitor in each case, i.e. fetal scalp electrode.

- Compare patient satisfaction between the monitoring systems

Inclusion criteria:

- 1) Maternal age >18 years old
- 2) Singleton pregnancy
- 3) Gestational age of 24 completed weeks or greater based on the estimated due date as calculated from last menstrual period or early ultrasound
- 4) Category I (reassuring) fetal heart rate tracing at time of enrollment

Exclusion criteria:

- 1) Fetal anomaly or chromosome defect
- 2) Allergy to silver
- 3) Woman with implanted electronic device of any kind
- 4) Irritated skin or open wound on the abdominal wall

Recruitment Mechanisms:

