**Statistics:**

Routine parametric and non parametric statistical analysis will be performed. Given that each patient serves as her own control (since we will be comparing the EUM device to the routinely used devices simultaneously), we will be able to limit the number of women enrolled.

To assess the improvement in continuity of readings in EUM, continuity in readings will be compared between EUM, Doppler, and FSE from the same patients. Assuming the number of minutes of unreadable tracing for the EUM is less than the Doppler by one minute, the standard deviation of difference in minutes by the two devices is three minutes, and there are two obstetrician readings per subject, to reach a power of 80% with 0.05 significance level, 39 patients will be needed for our primary outcome as listed below.

Regarding assessment of contractions, continuity in readings will be compared between EUM and IUPC in the same patients. To assess the improvement in continuity of readings in EUM, continuity in readings (yes or no) will be compared between EUM and

Version 5.13; June 19, 2020

IUPC from the same patients. A McNemar test will be used to compare the proportion of continuity between these two methods. With N=55 patients, the study will have at least 80% to detect an odds ratio of 3.2 associated with continuity between EUM and IUPC with a two-sided type I error rate of not more than 5%, assuming 50% of discordant pairs. It is acknowledged that the study has only adequate power to detect a substantial difference between EUM and Doppler, and between EUM and IUPC however, anything below this level would be of less clinical interest and the result we obtain from this study will be used to design more definitive studies in the future. Thus, the number of patients required to address each of the aims of the study is as below:

1. Fetal heart rate monitoring: EUM device v. external monitor v. FSE n = 39
2. Contraction monitoring: EUM device v. external monitor n = 55 obese and n = 55 nonobese subjects; EUM device v. intrauterine pressure catheter n = 55 obese and n = 55 nonobese subjects.
3. Productive v. non-productive contractions: EUM device v. external monitor n = 55 subjects.

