### Option 2 - EUM300 with dedicated notebook

The proposed setup eliminates the need to install the interface unit during the clinical evaluation time frame and minimize the required changes to the delivery room setup. The maternal unit will transmit the uterine activity/fetal heart rate information to an off-the-shelf computer equipped with Bluetooth V4.0 (e.g., Lenovo IdeaPad U41-70). An existing fetal monitor transmits similar information using HP-50 protocol over RS232 physical connection. The RS232 is likely to be connected to existing hospital IT. A simple Y connection is the only change needed to the delivery room. The RS232 transmissions will also be received by an off-the-shelf USB-RS232 adaptor.

Version 5.13; June 19, 2020

---

A computer program will record both the EUM300 and the fetal monitor into a common file (CSV format in order to be able to be analyzed by either Matlab or Excel). Program may also present the four signals (EUM Uterine, EUM FHR, monitor Uterine, monitor FHR) in real time. Other features may be: Dialog to provide the file information with patient ID, name, gestational age, etc.

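### The simultaneous three-way comparison of EUM, external and internal monitors cannot be computed from the recording described, and 39 and 55 are listed for contrasts they were not derived for

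*Combined protocol and SAP*

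**What the plan says.** **What is to be compared.** Objective 2 is "EUM device vs. external fetal Doppler vs. fetal scalp electrode (simultaneously obtained, 30 minute tracings will be compared"; Objective 1 has the same structure for contractions, with EUM, IUPC and external tocodynamometer. In Materials and Methods, the primary fetal heart rate (FHR) outcome is continuity "between EUM and fetal scalp electrode and external fetal heart rate monitoring from the same patient" and the primary contraction outcome is continuity "between EUM, IUPC and external tocodynamometer from the same patient". The Statistics section repeats the three-device, same-patient wording for FHR.

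**What is recorded.** Materials and Methods has each woman wear EUM together with either external or internal devices, whichever her care calls for. It says that "the data obtained from the two monitoring systems simultaneously will be compared". Device Description gives the file layout: "The file format is a simple 6 column format: Date, Time, EUM UA, EUM FHR, Monitor UA, Monitor FHR". The notebook set-up (Option 2) agrees: "Program may also present the four signals (EUM Uterine, EUM FHR, monitor Uterine, monitor FHR) in real time".

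**What is sized.** The Statistics section derives 39 from an assumed EUM-minus-Doppler difference of 1 minute, SD 3 minutes, two obstetrician readings per woman, 80% power and a 0.05 level. It then lists "Fetal heart rate monitoring: EUM device v. external monitor v. FSE n = 39". It derives 55 from a McNemar test of EUM against IUPC, and lists 55 obese and 55 nonobese women both for EUM v. IUPC and for EUM v. external monitor.

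**The concern.** The objectives and primary outcomes describe three instruments on one woman, with simultaneity stated in the objectives. The data capture describes two. If the trial runs as the capture is written, no 30-minute file can contain both the external and the internal signal, so the primary comparison as worded has no data set behind it.

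Two things follow. First, any statement that places EUM between the external and internal monitors would rest on different women or different times, not on each woman as her own control. Second, the listed sample sizes suggest planned power for EUM v. FSE and EUM v. tocodynamometer, for which the plan gives no inputs.

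Source matters as well. The variability outcome treats the internal monitor as the most accurate, so the analyst must know which signal a column holds. If the source is not logged at recording, it may be hard to recover later.

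**Working it through.** **1. Signals needed against signals held**

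- FHR: the three-way comparison needs 3 signals (EUM, Doppler, FSE). The file holds 2 (EUM FHR, Monitor FHR).
- Uterine activity: it needs 3 (EUM, tocodynamometer, IUPC). The file holds 2 (EUM UA, Monitor UA).
- Source of the monitor signal: none of the six columns carries it. Option 2 mentions a possible dialog for file information, but does not name the source among its examples.

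Each file therefore supports one EUM v. comparator pair for FHR and one for contractions. No section describes recording Doppler with FSE, or tocodynamometer with IUPC, at the same time.

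**2. What 39 was derived for**

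Inputs from Statistics: difference 1 minute, SD 3 minutes, two readings, 80% power, 0.05. The correlation ρ between a woman's two reading differences is not stated, nor is sidedness; I take two-sided.

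n = [(1.960 + 0.842) × 3 / 1]² × (1 + ρ)/2 = 70.6 × (1 + ρ)/2

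- ρ = 0: 35.3, so 36 (38 with the noncentral t).
- ρ = 0.1: 38.9, so 39 (41 with the noncentral t).

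So 39 is reproduced as a paired EUM v. Doppler size with nearly independent readings. Nothing in it refers to FSE.

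**3. What 55 was derived for**

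Inputs from Statistics: odds ratio 3.2, 50% discordant pairs, two-sided 5%, 80% power, EUM v. IUPC.

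- p10 = 0.5 × 3.2/4.2 = 0.381; p01 = 0.119; difference 0.262.
- n = [1.960 × √0.5 + 0.842 × √(0.5 − 0.262²)]² / 0.262² = 54.8, so 55.

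This is also reproduced, and it has no input for the tocodynamometer.

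**4. Illustration of what unequal comparator use would do**

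Assumptions: two independent readings (ρ = 0, the case most favourable to the plan), and the Doppler inputs carried over to FSE because the plan gives none. The SD of a woman's mean difference is 3 × √(1/2) = 2.12. Power is for a two-sided paired t-test of a 1-minute difference.

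| Pairs on one comparator | Power, ρ = 0 | Power, ρ = 0.1 |
|---|---|---|
| 39 | 82% | 78% |
| 30 | 70% | 66% |
| 20 | 52% | 48% |

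If 39 women divided 20/19 or 30/9, the smaller group could detect 1.44 or 2.26 minutes at 80% power (ρ = 0). The division is an assumption; the plan does not say how many women will have each device.

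**5. The contraction list**

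One recording with one UA channel can serve the tocodynamometer contrast or the IUPC contrast, not both. With one recording per woman, the list needs (55 + 55) + (55 + 55) = 220, which equals the stated ceiling. The plan explains that ceiling by a single set of 55 obese and 55 nonobese women, plus extra women for productive contractions.

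**The case against.** The strongest reply is that only wording is at fault. The Purpose section wants EUM to be similar to the internal devices and better than the external ones. That takes two EUM contrasts, each simultaneous and within woman, and the file can hold either. The contraction sizes are already listed as two pairwise comparisons. The electrodes stay on until delivery or discharge, so a woman could give an external segment early and an internal one later.

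Much of this stands. It shows that the pairwise design is workable, and it is the basis of the fix. It does not rescue the three-way comparison as worded: successive segments would not be the "simultaneously obtained, 30 minute tracings will be compared" of Objective 2, and the plan does not describe them.

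A reader might go further and infer three things that the documents do not support.

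- *That 39 cannot be reached.* The 39 are EUM v. Doppler pairs, which this set-up can record. Only their use for a comparison with FSE is unsupported.
- *That the trial is badly underpowered because 39 women must be shared between Doppler and FSE.* The plan foresees 110 women for contractions and up to 220 in all, with overlapping FHR monitoring. Since 39 + 39 = 78 fits within 110, both contrasts could reach 39. Nor should power be worked out from one value per woman; the plan specifies two readings, and whether they justify 39 is a separate question.
- *That the source goes unrecorded.* This is shown for the six listed columns only. The optional dialog, the clinical systems named under Data management or another study record might hold it. The plan does not say so.

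**Conclusion.** The point holds as a contradiction between what the plan sets out to compare and what it describes recording. As described, the three-way simultaneous, same-woman comparison cannot be computed: two signals of each type are held where three are needed. Pairwise comparisons of EUM with one comparator can be.

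The sample sizes are sound only for the contrasts they came from: 39 for EUM v. Doppler (given nearly independent readings) and 55 for EUM v. IUPC. EUM v. FSE and EUM v. tocodynamometer have no inputs, so no stated power applies to them.

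The loss of power cannot be fixed from the documents. The range from 82% at 39 pairs to 52% at 20 is an illustration that rests on an assumed split, independent readings and the Doppler inputs. The finding does not depend on it. This should be corrected, because it changes what the trial may conclude about EUM relative to both types of monitor.

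**What to change.** 1. Restate Objectives 1 and 2 and both primary outcomes as separate simultaneous within-woman contrasts: EUM v. external and EUM v. internal. Alternatively, keep the three-way comparison and specify how both comparators are recorded at once.
2. Label 39 as the size for EUM v. Doppler and 55 as the size for EUM v. IUPC. For EUM v. FSE and EUM v. tocodynamometer, state the precision expected from the women available (up to 220), and claim no 80% power.
3. Add an FHR-source column (Doppler/FSE) and a UA-source column (tocodynamometer/IUPC) to each file, with switch times. Analyse only segments with one source throughout.
4. Make no within-woman external v. internal claim unless both signals are recorded.

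The cost is two columns in the recording program and edits to the objectives, primary outcomes and sample-size list. The drawback is that the three-way simultaneous claim is dropped, and any segment in which the source changes is excluded.

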**Data management:**

Data collected in this study protocol will be extracted from the secure password protected clinical computer programs utilized by Montefiore for patient care: ASOBGYN/EPFweb/EPIC. Information extracted for study use will be maintained in a locked office on a password protected computer and not accessible to others. Once the clinical information obtained on a patient is completed the information will be de-identified. Patient confidentiality will be maintained at all times.

**Statistics:**

Routine parametric and non parametric statistical analysis will be performed. Given that each patient serves as her own control (since we will be comparing the EUM device to the routinely used devices simultaneously), we will be able to limit the number of women enrolled.

To assess the improvement in continuity of readings in EUM, continuity in readings will be compared between EUM, Doppler, and FSE from the same patients. Assuming the number of minutes of unreadable tracing for the EUM is less than the Doppler by one minute, the standard deviation of difference in minutes by the two devices is three minutes, and there are two obstetrician readings per subject, to reach a power of 80% with 0.05 significance level, 39 patients will be needed for our primary outcome as listed below.

Regarding assessment of contractions, continuity in readings will be compared between EUM and IUPC in the same patients. To assess the improvement in continuity of readings in EUM, continuity in readings (yes or no) will be compared between EUM and

Version 5.13; June 19, 2020

IUPC from the same patients. A McNemar test will be used to compare the proportion of continuity between these two methods. With N=55 patients, the study will have at least 80% to detect an odds ratio of 3.2 associated with continuity between EUM and IUPC with a two-sided type I error rate of not more than 5%, assuming 50% of discordant pairs. It is acknowledged that the study has only adequate power to detect a substantial difference between EUM and Doppler, and between EUM and IUPC however, anything below this level would be of less clinical interest and the result we obtain from this study will be used to design more definitive studies in the future. Thus, the number of patients required to address each of the aims of the study is as below:

1. Fetal heart rate monitoring: EUM device v. external monitor v. FSE n = 39
2. Contraction monitoring: EUM device v. external monitor n = 55 obese and n = 55 nonobese subjects; EUM device v. intrauterine pressure catheter n = 55 obese and n = 55 nonobese subjects.
3. Productive v. non-productive contractions: EUM device v. external monitor n = 55 subjects.

Because many of these patients will overlap due to the fact that they will serve as their own control and will be monitored simultaneously for fetal heart rate and change in cervical exam, it is anticipated that the maximum number of patients required in this study will not be more than 220 patients since 55 obese and 55 non-obese patients will be needed and additional patients may be needed to evaluate productive contractions. In addition to comparing the continuity in readings, in assessing contractions, we will also compare average frequency of contractions, the duration of contraction, maximum height of the contraction, the total Montevideo units obtained, the timing of the contraction and the amount of discontinuous tracings from the devices. In assessing fetal heart rate, we will compare average fetal heart rate, baseline heart rate, the number accelerations, the number of decelerations, the timing of the accelerations, the timing of decelerations, the maximum fetal heart rate achieved during acceleration, the lowest fetal heart rate achieved during deceleration, and compare the degree of variability in the tracing. A continuous outcome will be compared using a paired t-test.

Version 5.13; June 19, 2020

As each patient is serving as its own control, missing data is unlikely to be an issue in this study once the patient consents. If the monitoring is less than 30 minutes, these patients will not be used in analysis due to concern for completeness and accuracy.

Safety assessment:

Safety and tolerability will be assessed by recording of adverse events. Adverse events will be reported. Adverse events will be assessed in terms of their seriousness, severity, and relationship to the study device. To date more than 800 patients have used the device in clinical trials and there have been no safety events reported with the use of the device to date.

Potential benefits:

There is no immediate benefit to the subject from her participation in this study. The study results will support the development of the EUM300pro system, which may have clinical importance in providing the care provider with more continuous and accurate monitoring of fetal heart rate and contractions in a less invasive way. These parameters will aid the medical staff in making timely clinical decisions and increasing the chances of attaining a successful treatment and/or delivery.

Potential risks:

No severe or serious events are anticipated with the use of the EUM300 system. There is a potential for an allergic reaction to the EUM adhesive.

Alternatives:

Patients may choose not to participate in the study or withdraw from the study at any time for any reason without compromise or change in their care.

Adverse Events:

Definition of Adverse Events (AE)

An AE is any reaction, side effect, or other untoward event (signs, symptoms, and changes in laboratory data) associated with the use of a test article (drug, biologic, or device),

Version 5.13; June 19, 2020

whether or not the event is considered related to the test article. All AE occurring after the administration of study treatments will be recorded. AE will be ascertained on the basis of volunteered symptoms and clinical observation and assessment at study visits. AE and concomitant medication information will be recorded during study visits on the appropriate case report form (CRF) page, and every effort will be made to capture information regarding AE and concomitant medications between visits. All AE considered to be related to study treatment, and all serious AEs (SAE) will be followed until resolved or until a stable status has been achieved.

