#### Purpose:

We propose to perform a study to validate the accuracy and clinical usefulness of the EUM device by comparing it with simultaneous use of current methods (both external or internal devices) among obese patients and patients with normal body mass indexes (BMI). Our goal is to show that the EUM device is a noninvasive tool of similar utility to the fetal scalp electrode and the IUPC, and superior the traditionally used noninvasive devices (Doppler ultrasound and tocodynamometer).

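### The 39 women for the heart-rate continuity outcome give 80% power only if the correlation between the two obstetricians' readings is at most 0.05 (two-sided) or 0.35 (one-sided), and the plan states neither the correlation nor the sidedness

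*Combined protocol and SAP*

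**What the plan says.** The Statistics section sizes the heart-rate continuity outcome on the EUM v. Doppler contrast. The target is directional: "Assuming the number of minutes of unreadable tracing for the EUM is less than the Doppler by one minute". The variability and replication inputs are that "the standard deviation of difference in minutes by the two devices is three minutes, and there are two obstetrician readings per subject". The result is that "to reach a power of 80% with 0.05 significance level, 39 patients will be needed for our primary outcome". Materials and Methods repeats the calculation: "there are 2 obstetrician readings per subject, to reach a power of 80% with 0.05 significance level, 39 patients will be needed". The list of numbers by aim, also under Statistics, carries it forward: "Fetal heart rate monitoring: EUM device v. external monitor v. FSE n = 39".

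The same section assigns a paired t-test to continuous outcomes but does not say how two readings per woman enter that test. The only statement of sidedness, "with a two-sided type I error rate of not more than 5%, assuming 50% of discordant pairs", belongs to the separate McNemar calculation for contractions. The Purpose section frames the aim directionally, as showing that EUM is "superior the traditionally used noninvasive devices (Doppler ultrasound and tocodynamometer"). No section gives a correlation or agreement figure for the two readings.

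**The concern.** A second reading of a woman's recordings adds information only to the extent that it differs from the first for reasons unrelated to the woman. If two obstetricians largely agree on how many minutes are unreadable on each device, the second reading adds little, and the sample size should be close to that for one reading per woman. Counting the readings as nearly independent comes close to halving the requirement.

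The stated power belongs to a primary outcome. If it holds only under an assumption that nobody has written down, a non-significant EUM v. Doppler result from about 39 women could be taken as evidence against a 1-minute gain when the study had little more than an even chance of detecting one.

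**Working it through.** **Inputs from the plan.** Difference 1 minute; SD of the device difference 3 minutes; 2 readings per woman; power 80%; significance level 0.05 (Statistics; Materials and Methods). Test: paired t (Statistics).

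**Inputs not in the plan.** The between-reader ICC of the EUM-minus-Doppler difference is shown over its full range, 0 to 1. Sidedness is shown both ways. SD 3 is taken as the SD for one reading, because that is the reading that fits 39.

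**Step 1: one difference per woman.** By the normal approximation, n = (z_alpha + z_0.80)² × SD² / difference².
- Two-sided: (1.960 + 0.842)² × 9 = 70.64, so 71; with the noncentral t, 73.
- One-sided: (1.645 + 0.842)² × 9 = 55.64, so 56; with the noncentral t, 58.

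Neither is near 39, so the reduction must come from the second reading.

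**Step 2: reproduce the 39.** The variance of the mean of two readings is 9 × (1 + ICC)/2. At ICC 0 this is 4.5 (SD 2.121). Two-sided n is then 35.32, so 36 (normal), or 38 (t), and 39 women have 82% power. The figure is therefore reproducible and is not an arithmetic slip. A result of exactly 39 arises two-sided at ICC about 0.03–0.04 (t) or 0.08–0.10 (normal), and one-sided at about 0.32–0.35 (t) or 0.37–0.40 (normal). The number alone does not show which assumption was made.

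**Step 3: largest ICC at which 39 women keep 80% power (paired t).**
- Two-sided: the SD of the mean must be at most 2.17, so ICC at most 0.049.
- One-sided: the SD of the mean must be at most 2.47, so ICC at most 0.352.

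**Step 4: consequence over the range (paired t on the mean of two readings).**

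| ICC | SD of mean | Two-sided power, n = 39 | Women for 80%, two-sided | Detectable difference, n = 39, 80%, two-sided (min) | One-sided power, n = 39 | Women for 80%, one-sided |
|---|---|---|---|---|---|---|
| 0 | 2.121 | 82% | 38 | 0.98 | 89% | 30 |
| 0.2 | 2.324 | 75% | 45 | 1.07 | 84% | 35 |
| 0.5 | 2.598 | 65% | 55 | 1.20 | 76% | 44 |
| 0.8 | 2.846 | 57% | 66 | 1.31 | 70% | 52 |
| 1.0 | 3.000 | 53% | 73 | 1.38 | 66% | 58 |

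**Step 5: if more women are analysed.** Two-sided power for 1 minute at ICC 0 / 0.5 / 1.0 is 93% / 80% / 68% with 55 women, 98% / 90% / 80% with 73, and over 99% / 98% / 93% with 110 (the 55 obese plus 55 nonobese women planned for the external contraction comparison).

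**The case against.** The strongest reply is that the plan never limits the heart-rate analysis to 39 women. The only rule that drops a woman from analysis is monitoring shorter than 30 minutes, the Statistics section expects the aims to share patients, and total enrolment may reach 220. On that reading 39 is a minimum, and with 73 women 80% power is reached even at ICC 1.0. This stands, and it makes the shortfall conditional. It does not supply the missing assumption, nor does it guarantee the larger number. Standard monitoring is external or internal as clinically indicated (Materials and Methods), and the data file has a single column for the standard monitor's heart rate (Device Description), so women on a scalp electrode may have no Doppler signal.

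The plan also concedes limits: "It is acknowledged that the study has only adequate power to detect a substantial difference between EUM and Doppler". It adds that smaller effects matter less and that the results will inform later studies. That tempers how a null result should be read, but the calculation itself sets the target at 1 minute, so the concession does not explain the 39.

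Three stronger readings are tempting, and the documents do not support them:
- *The 39 is a miscalculation.* It is not; see Step 2.
- *The assumption is demonstrably optimistic because both obstetricians read the same tracing.* The plan says only that there are two readings per subject. A shared tracing is likely, and would make an ICC near zero implausible, but this is inference. One-sided, the tolerated ICC of 0.35 is not near zero.
- *SD 3 may describe the mean of two readings, so 73 or 58 women are needed whatever the ICC.* The wording does not exclude this, but those inputs would not have produced 39, so the plan's own result points to an SD per reading.

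**Conclusion.** The point holds as an undocumented assumption behind a primary-outcome power statement. The second reading carries the step from 73 (two-sided) or 58 (one-sided) down to 39, and what it is worth depends on an ICC that the documents do not give. At an ICC of 0.5, for illustration, 39 women fall 15 percentage points short of 80% two-sided and 4 points short one-sided; at ICC 1.0 the shortfalls are 27 and 14 points.

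This rests on SD 3 being per reading, one averaged value per woman, the paired t-test, and about 39 women being analysed. It should be fixed, because the repair is specific and cheap. It does not show that the study as enrolled will be underpowered.

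**What to change.** 1. In Materials and Methods and in Statistics, state the sidedness and the assumed ICC, and restate the figure over a range. If the test is two-sided, for example: *With 39 women, a two-sided 0.05 paired t-test on the mean of the two readings (SD 3 minutes per reading) has 82%, 65% and 53% power for a 1-minute difference at ICC 0, 0.5 and 1.0, and 80% power for 0.98, 1.20 and 1.38 minutes.*

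2. In Statistics, beside the paired t-test and the 30-minute rule, add: *The EUM v. Doppler heart-rate comparison uses every enrolled woman with 30 minutes of simultaneous EUM and Doppler monitoring, whatever the amount of unreadable tracing, with one value per woman (mean of the two readings), so that two readings are not counted as independent women.* The criterion should be time monitored and not completeness of the tracing, because excluding women with signal loss would select on the outcome.

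3. Report the number of women who actually have both signals, and the power that number supports (Step 5).

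**Cost.** Wording changes, and extra readings of tracings already recorded. At 2 devices × 2 readers per woman, that is (55 − 39) × 4 = 64 readings for 55 women, or (110 − 39) × 4 = 284 for 110. No enrolment beyond plan is needed. The downside is a less favourable stated power for 39 women unless the ICC is low enough (at most 0.05 two-sided or 0.35 one-sided).
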